Specific aim #1: Define functional nausea (FN) as an entity subdivided by measures of arousal, anxiety and gastric motor function.

Hypothesis: Adolescents with chronic nausea form subgroups based on clinical, physiologic and psychological parameters: 1) FN: characterized by high anxiety and emotional arousal, autonomic imbalance/low vagal tone and absence of major foregut dysmotility, 2) gastroparesis, and 3) poor gastric compliance. We will separate FN from other groups by clinical questionnaires, autonomic tests (heart rate variability) and gastric motility tests (gastric emptying, accommodation tests).

Specific aim #2: Demonstrate that resting state functional brain connectivity is different in female adolescents with FN compared to gender and age-matched healthy controls.

Hypothesis: Adolescents with FN will have altered rsFC between brain regions associated with emotional arousal neurocircuits (amygdala) and the top-down regulation of these by the prefrontal cortex. There will be decreased resting state functional connectivity between the ventromedial prefrontal cortex (vmPFC) and amygdala in adolescents with FN compared to healthy controls.

Specific aim #3: Demonstrate that four weeks of auricular neurostimulation improves nausea while strengthening the vagal tone and the abnormal resting state brain connectivity in female adolescents with FN compared to baseline and to more resemble that of healthy controls.

Hypothesis: 3a) Compared to baseline (pre-stimulation), there will be reduction in nausea and concurrent symptoms in the active compared to sham neurostimulation group after 4 weeks of therapy. 3b) Active neurostimulation therapy will increase vagal tone compared to baseline and also increase the rsFC between the vmPFC and amygdala in female adolescents with FN.

C. BACKGROUND, SIGNIFICANCE, AND RATIONALE

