Participants who are interested in learning more about the fMRI sub-study will indicate so on the main study consent form. A member of the research team will explain the sub-study to the participant and guardian(s). If the participant is willing to participate, the sub-consent and assent forms will be completed. [name] will complete a psychological history for all participants who agree to participate in the fMRI sub-study. Female participants in the experimental group (Nausea group; n=15 and IBS group; n=15) who are found to be eligible to participate in the sub-study will be scheduled to complete the fMRI scans at Visit 3 (baseline scan) prior to EAD placement and Post #1 (post-scan; day 5 after the last neurostimulator placement within one hour of removing the device). The post-scan will be compared to baseline and baseline scans from 15 age-and gender-matched healthy controls who will undergo one fMRI scan (no therapy). All ethnic categories will be included.

Healthy control participants will be recruited via word of mouth. Researchers will mention the study to peers who will be instructed to contact the research team to learn more about the study. A member of the research team will introduce the study either in person or over the phone and will explain the inclusion and exclusion criteria. If the participant is eligible, consent/assent documents will be completed. Participants will then be scheduled to visit the pTRU where they will meet with a study physician who will perform a brief medical examination to confirm participant eligibility. Eligible participants will be escorted to the MRI unit by a member of the research team where they will be introduced to the mock scanner. Participants will have the option of lying in the mock scanner prior to their fMRI scan. A medical professional who is a member of the research team will be present during the scan. Healthy controls will only have 1 fMRI visit which will be completed at their convenience.

fMRI Sub-study inclusion (FN and IBS Groups):

- meet general study inclusion criteria

fMRI Sub-study inclusion (Healthy Control Groups):

- Female children, aged 12 years to 18 years, who provide written assent and whose parents provide written permission for participation
- English-speaking

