- Subjects who have no previous disorders or history, symptoms or signs of gastrointestinal disorder, fibromyalgia, chronic fatigue syndrome, migraine, chronic dizziness while upright, PTSD, panic disorder, functional gastrointestinal disorders, constipation or fecal incontinence, diagnosis of postural tachycardia syndrome, diabetes, asthma, neuropathy
- Subjects who have not seen by a gastroenterologist within 2 years of enrollment at the discretion of the PI.
- Subjects who have no chronic gastroenterology complaint

fMRI Sub-study exclusion (All Groups):

- Currently receiving any medication that will strongly affect fMRI results
- Patients with pacemakers, metal clips used in previous surgery or other device which are not compatible with MRI scanning (for sub-study group only)
- Inability to lie still in the scanner (for sub-study group only)
- Claustrophobia or inability to lie still in the scanner (for sub-study group only)
- Orthodontic braces or permanent retainers (for sub-study group only)
- Patients who are unable to tolerate noise produced by the MRI

Visit 3: Following completion of the questionnaires, subjects who wish to do a mock scanning, will be scheduled for a 30-minute test fMRI session in the mock scanner. If the subject tolerates this, they will complete the fMRI scan. When fMRI scan is completed, subjects in the experimental group will have the neurostimulator placed (see section on placement details) by a study investigator who is a certified MD.

Post #1: Subjects in the fMRI sub-study (FN or IBS groups) will return to the scanner to complete their final fMRI scan on day 5 of last week of therapy, after removal of the EAD device.

E. TOTAL NUMBER OF HUMAN RESEARCH PARTICIPANTS PROPOSED FOR THIS STUDY AT THIS SITE AND GLOBALLY. WHAT ARE THESE NUMBERS BASED ON?

We aim to enroll 80-100 adolescents with chronic nausea for phenotyping with tests and clinical questionnaires followed by randomization to neurostimulation or sham therapy. A subset of 15 adolescent females and 15 age-matched females with IBS will enter a sub-study involving the same procedures as well as pre and post treatment fMRI scans. Baseline fMRI data will be compared to scans obtained in 15 healthy, age and gender matched healthy controls.

F. DRUGS OR PROCEDURES

Table 1.

| | Pre | Visit 1 | Visit 2 | Visit 3 | Visit 4-5 | Visit 6 | Post #1 | Post #2 |
|--|-----|---------|---------|----------------|-----------|----------------|---------|---------|

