Subjects will enter a 4-week, prospective randomized, double blind sham controlled treatment trial with the FDA-approved and commercially available EAD manufactured by Key Electronics (Jeffersonville, IN, USA) and distributed by Innovative Health Solutions (Versailles, IN, USA). The device is cleared under the BWK classification, with intended use in the practice of acupuncture by qualified practitioners of acupuncture as determined by the states. EAD is an ambulatory, neurological device which consists of a battery powered, externally affixed generator with 4 wire leads attached to 3 electrode/ needle arrays and one single point needle. The arrays are designed to produce a field effect similar to surgically implanted peripheral neurostimulators. The electrodes will be placed percutaneously in the external ear with the help of a transilluminator to visualize the neurovascular bundles. Three electrodes will be placed on the ventral and one on the dorsal aspect of the ear. The electrodes will be taped and secured behind the ear next to the generator itself which is secured to the skin with adhesive. The entire device may be covered by longer hair. The placement of the devices is within standard of care by properly trained medical doctors as already completed trial at CHW (IRB# 689519-17). Training of MDs has been performed by [name] or [name] as representatives of Innovative Health Solutions. Training of other involved physicians may be performed if protocol approved. 40-50 subjects will receive the active EAD device while 40-50 subjects will receive an inactive device that is identical to the active device but lacking the battery.

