Subjects will be randomized in a 1:1 ratio to either treatment or sham group. Randomization will be determined using a computer program based on random number generation in blocks of 10 subjects at a time. The manufacturer will provide the researchers with four devices per package (4 weeks per patient) and distribute 10 packages at a time to the investigators. Each package will have a serial number and only one research coordinator will have the key to which serial numbers represent active devices and which represent inactive ones. This research coordinator will keep the data in a secure database and will not be involved in any of the patient recruitment or study procedures. All other research coordinators, investigators, statistician and nurses involved will be blinded. Research coordinators within the division of gastroenterology will store the devices as pre-packaged by manufacturer and label the devices with a serial number and patient ID number. A labeled folder for each patient with all questionnaires needed for the entire study will also be kept with each subject package. The devices and folders will be stored in a locked office in the gastroenterology division, only accessible by research coordinators. Password protected iPads will be used to collect questionnaire information from participants. No PHI will be loaded on these iPads.

A blinded research coordinator will bring each subject's numbered package to the research area (Translational Research Unit) when patient arrives. The package for the subject will be stored locked in the TRU until the subject finishes the 4 week therapy. The coordinator will ask the subject to complete the pre-placement questionnaires (Table 1; visit #3) and hand the device (numbered with serial # and patient ID only) to one of the certified MDs for placement. The devices will be "made to order" when requested by the PI and will be shipped packaged as above.

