The fMRI scans will be carried out using GE 3T short bore scanner. This scanner is located at the Froedtert Hospital. For each participant we will perform one baseline whole brain anatomical scan and one resting state fMRI scan before and after therapy. Healthy controls will have only one baseline fMRI scan. The healthy controls will also undergo a visual task where they are simply shown images while in the fMRI scanner. These images will be related to toilet training and this data will be used for healthy comparison data from separate study by our group (IRB #774802-6). We anticipate the whole session to last about 40 minutes. Echo planner images resolved to 64x64 pixels/slice at TR of 2s and echo time of 25 ms will be obtained.

Resting State Functional Connectivity MRI

Resting state functional connectivity (rsFC) analysis measures the temporal correlation between a predetermined seed region of interest and functionally related brain regions. After subgrouping and additional consenting, 15 post-pubertal female subjects classified as FN will undergo a 10 minute anatomical scan followed by a 6 min rsFC MRI scan at baseline prior to first EAD placement which is repeated after 4 weeks of therapy (after stimulator removed) (Table 1; post-neurostimulation #1). 15 female subjects classified as irritable bowel syndrome (IBS group) will undergo the same protocol. Resting state MRI scans will be performed per protocol below. The amygdala will be used as a seed region and the functional connectivity between the amygdala and PFC regions will be examined during rest at baseline. Data will be compared in treatment

responders (if possible) and non-responders in order to evaluate connectivity differences before and after therapy in these two groups.

Multimodal Imaging protocols

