All these imaging protocols and data acquisition will be completed within one scanning sessions in 30 min for each subject.

Data Acquisition and Analysis

Data acquisition: The cerebral cortical activity will be monitored in all subjects with a blood oxygenation level-dependent (BOLD) fMRI technique. Gradient echo-planar imaging (EPI) data will be acquired on a Neuro-optimized 3.0 T MR system (General Electric, Milwaukee, WI, USA). A quadrature birdcage head coil will be used for radio frequency (RF) transmission and reception. One hundred and twenty T2*- weighted images depicting blood oxygenation level-dependent (BOLD) contrast (Ogawa et al., 1990) will be acquired over 6 min at each of 14 near-axial non-contiguous 4 mm thick planes parallel to the inter commissural (AC±PC) line: TE (echo time) = 25 ms; TR (repetition time) = 2 s; matrix size = 64 x 64; FOV (Field of view) = 240 mm; in-plane resolution = 3.75*3.75 mm²; interslice gap = 0.7 mm.

Scanning protocol: A 6 min resting state scan will be performed at baseline. The same protocol is repeated at end of therapy with another scan after device is removed (Table 1; post-neurostimulation #1). This will allow us to examine functional connectivity changes induced by the stimulation. rsFC will be compared between baseline and end of treatment in both treatment responders and non-responders and compared to healthy controls and IBS patients. Brain activation will be quantified for each voxel by measuring percent change of BOLD signal relative to the baseline. Spatial smoothing of the response magnitude across voxels will be

conducted using a 6-mm full-width half-maximum (FWHM) Gaussian kernel filter to compensate for intersubject variability. In the group analysis, activation maps for each stimulation state and group will be derived by applying voxelwise one-sample *t*-tests of fitting coefficient from regression analysis. The obtained statistical maps were corrected for multiple comparisons using the probability and cluster thresholding technique (AlphaSim in AFNI).

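### No planned connectivity analysis uses the randomised arm, so the connectivity part of hypothesis 3b is not tested as written; separately, the scan figures (120 images, TR 2 s, 6 min) do not agree

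*Combined protocol and SAP*

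**What the plan says.** Section B, hypothesis 3b, states that active therapy will "also increase the rsFC between the vmPFC and amygdala in female adolescents with FN". Section E has the nausea patients phenotyped, "followed by randomization to neurostimulation or sham therapy", and the treatment protocol in section F adds: "Subjects will be randomized in a 1:1 ratio to either treatment or sham group". The fMRI subset follows the same procedures with scans added.

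Under Power, Aim 3, a sham comparison is given for vagal tone, and the reader is sent to the fMRI section for connectivity. The longitudinal connectivity comparisons in the document are:

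- **Section D, Optional fMRI Sub-study:** "The post-scan will be compared to baseline and baseline scans from 15 age-and gender-matched healthy controls".
- **Section F, Resting State Functional Connectivity MRI:** responders and non-responders are compared "in order to evaluate connectivity differences before and after therapy in these two groups".
- **Section F, Scanning protocol:** "rsFC will be compared between baseline and end of treatment in both treatment responders and non-responders and compared to healthy controls and IBS patients". The same paragraph says the repeat scan will show connectivity changes caused by the stimulation. It then specifies voxelwise one-sample t-tests.
- **Section F, fMRI analyses:** a discriminant function separating normal from diseased subjects, and a multivariate regression of clinical scores (later described as cognitive ability) on imaging parameters. This section also claims a biomarker for measuring treatment efficacy.

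On acquisition, the Data acquisition paragraph gives 120 images, a TR of 2 s and a duration of 6 min together. The Optional fMRI sub-study text in section F repeats the TR: "at TR of 2s and echo time of 25 ms will be obtained". The 6 min duration appears three times: once under Resting State Functional Connectivity MRI, once under Data acquisition and once under Scanning protocol.

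**The concern.** The trial has a randomised sham control and scans patients before and after treatment, yet no connectivity analysis uses the allocation. Post versus baseline on the scanned girls pools active and sham patients. Responder status is observed after randomisation and can arise in either arm, so a responder/non-responder split does not recover the randomised comparison. Healthy controls are scanned once and untreated, so they cannot show what repeat scanning or time alone would do.

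At stake is the mechanistic claim of Aim 3. A rise in connectivity found by the stated contrasts could be reported as a device effect when it would have occurred under sham too.

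The scan-length mismatch is a separate and smaller matter. It leaves unclear how long a time series each connectivity estimate rests on.

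**Working it through.** **Does any analysis use the arm?** The documents give no power or effect-size figure for rsFC, so there is nothing to reproduce here. Each analysis was read for an arm term:

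| Analysis (section) | Contrast | Arm used? |
|---|---|---|
| Post-scan (D, Optional fMRI Sub-study) | own baseline; healthy controls | no |
| Resting state (F) | responders, non-responders | no |
| Scanning protocol (F) | pre/post by response; controls; IBS | no |
| Voxelwise maps (F) | one-sample, per stimulation state and group, both undefined | no contrast |
| Discriminant (F, fMRI analyses) | normal versus diseased | no |
| Regression (F, fMRI analyses) | clinical scores on imaging parameters | no |
| MMRM (F, Longitudinal Continuous Variables) | treatment, visit, interaction | yes, but rsFC is not named |

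**What an arm contrast could detect.** Inputs: 15 FN girls scanned (sections D to F). Assumptions: a 7:8 split, two-sided 5%, 80% power, no dropout.

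- Two-sample t-test (noncentral t, 13 df): smallest detectable difference 1.57 SD. Power is about 30% at 0.8 SD and 15% at 0.5 SD.
- ANCOVA on the baseline scan: 1.580 (the same calculation with 12 df) × √(1 − r²), where r is the assumed pre/post correlation. For r = 0.3, 0.5 and 0.7 this gives 1.51, 1.37 and 1.13 SD.
- With the 12% dropout used under Power, 15 × 0.88 ≈ 13. A 6 v 7 comparison detects 1.71 SD unadjusted.

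**The split is not controlled within the sub-study.** Drawing 15 at random from 40 active and 40 sham (hypergeometric) gives 7:8 with probability 0.43 and 5:10 or worse with probability 0.25. From 50:50 these are 0.42 and 0.26. A 5:10 split detects 1.66 SD. This assumes that scan uptake is unrelated to arm and that scanned girls are scattered across enrolment.

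**What pre/post testing would credit to the device.** Assume a non-specific change of d SD of the change score, equal in both arms, and one connectivity measure tested at an uncorrected two-sided 5%. The paired t-test has noncentrality d√n with n − 1 df.

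| Test | d = 0.5 | d = 0.8 |
|---|---|---|
| All 15, post versus baseline | 44% | 82% |
| Active only, n = 7 | 20% | 43% |
| Active only, n = 8 | 23% | 50% |
| Active versus sham | 5% | 5% |

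**Scan length.** 120 images × 2 s = 240 s = 4 min, against the stated 6 min. Ten discarded volumes would add only 20 s (4.33 min), and two TRs per image would give 8 min. Six minutes needs 360 / 2 = 180 images at TR 2 s, or 360 / 120 = 3 s per image with 120 images.

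**The case against.** The strongest reply is that hypothesis 3b names baseline, not sham, as the comparator for its connectivity part. On that reading the plan's pre/post comparison is nearly the intended test. It is true that adopting active versus sham goes a step beyond the hypothesis as worded. But even the baseline-only reading needs the active patients picked out, and the plan does not do so. An active-only pre/post test would still not separate the device from sham response.

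Two passages might be thought to supply the arm. The MMRM has treatment and treatment-by-visit terms. However, it is described for efficacy variables with nausea and pain as examples, and the Power section sends rsFC elsewhere. The voxelwise maps are to be made per stimulation state and group, but neither term is defined. Pre/post and FN/IBS/control fit as well as active/sham, and one-sample tests compare nothing across groups.

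Some limits on the figures do stand:

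- The rejection rates assume a single measure without correction. They are not the rates for the planned cluster-corrected maps.
- The 25% chance of a 5:10 or worse split depends on how scanned girls are spread over enrolment. If they were 15 consecutive enrolees starting with a block of 10 balanced 5:5, the last five would all have to fall in one arm: 2 / C(10,5) = 2/252, about 0.8%.
- Whether IBS patients are randomised is unclear. Section D says all subjects receive stimulation or sham, and section E gives the IBS girls the same procedures. Yet section F says "40-50 subjects will receive the active EAD device while 40-50 subjects will receive an inactive device", which adds up to the 80-100 nausea patients alone.
- The sub-study is optional and small, so the added contrast will be imprecise. That is a reason to report an interval, not to rely on uncontrolled contrasts.

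**Conclusion.** The concern holds on both parts.

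No specified rsFC analysis uses the randomised allocation, so the plan as written gives a confounded answer to the connectivity part of hypothesis 3b. This conclusion comes from the text alone and needs none of the numerical assumptions. The rejection rates and detectable differences rest on assumed inputs and show scale only: pooled pre/post testing could often credit a shared change to the device, while the arm contrast in FN girls can reliably detect only large effects.

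The image count, TR and scan length are mutually inconsistent by 2 min in 6. The documents do not show which figure is wrong.

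This should be fixed, but it is confined to the imaging sub-study.

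**What to change.** 1. Make the imaging test for hypothesis 3b active versus sham in the FN girls: ANCOVA of the post-scan amygdala-vmPFC Fisher z on baseline z and arm. Report a confidence interval and state the limited precision. Reword the hypothesis so that sham is its comparator.
2. State whether IBS patients are randomised, reconciling sections D and E with the treatment protocol in section F. If they are, a model of FN plus IBS with diagnosis as a factor can be supportive only.
3. Label the responder/non-responder comparisons exploratory.
4. Name the Aim 2 test, a two-sample comparison of baseline z in FN versus healthy controls, and keep the one-sample maps as descriptive.
5. Reconcile image count, TR and scan length across the acquisition paragraphs. In the same pass, reconcile the coil and echo descriptions: Multimodal Imaging protocols gives a 32-channel coil and a multi-echo approach, while Data acquisition gives a birdcage coil and a single echo time.

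The cost is SAP wording and corrected acquisition details. Allocation is already recorded and the scans are already planned, so no extra scans or patients are needed.

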The vmPFC regulates autonomic responses in which lower vmPFC activity reflects vagal withdrawal.⁵⁷ Numerous fMRI studies show increased vmPFC with concomitant decreased amygdala activity during successful emotional regulation, suggesting that the *strength of vmPFC-amygdala coupling predicts healthier regulation of emotions and anxiety*.^{8,58-60} A developmental switch occurs during adolescence when there is a normal reduction in amygdala reactivity due to top-down mPFC control over amygdala.⁶¹ Preliminary fMRI connectivity analysis by our group shows impaired vmPFC, amygdala and hippocampal connectivity with the hypothalamus in adolescents with FGIDs. The emotional arousal network with amygdala as a key node is activated by perceived or real perturbation of body homeostasis.⁶² Abnormal emotional arousal with poor feedback inhibition of amygdala by the vmPFC and altered ANS output results in heightened anxiety, lower vagal tone and morning symptoms upon awakening. Nausea coupled with anxiety is thus likely a manifestation of dysregulated emotional arousal and resulting impaired corticolimbic modulation of gut sensations. **We hypothesize that there is aberrant top-down control by the vmPFC on amygdala activity, characterized by decreased rsFC between these regions in adolescent females with FN.** Modulating brain signals that communicate discomfort such as nausea by means of peripheral neurostimulation may influence these specific brain regions and provide clues to underlying pathophysiology and physiology-based treatment.

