We will assemble these measurements for each of the n subjects into the $n \times m$ matrix \mathbf{Y} . The design matrix \mathbf{X} is an $n \times p$ matrix, $\mathbf{X}_j(t) = [X_{j1}(t) \ X_{j2}(t) \ \dots \ X_{jp}(t)]$. In this case, the regression coefficients, which relate the independent to the dependent variables, are represented by the $p \times m$ matrix $\boldsymbol{\beta}$. Then, the multivariate linear regression model is given by: $\mathbf{Y} = \mathbf{X}\boldsymbol{\beta} + \boldsymbol{\varepsilon}$, where $\boldsymbol{\varepsilon}$ is the error matrix. The error terms corresponding to the m cognitive observations for the j th subject may be correlated. Likelihood ratio tests will be performed to assess the statistical significance of various components of the regression coefficient matrix $\boldsymbol{\beta}$, in order to determine which subsets of the independent variables can be used to predict variations in cognitive ability across subjects.

MCW Research Team and imaging facility: MCW is a national leader with a well-established model for basic and clinical translational research. Our MCW research group was the first to discover and develop R-fcMRI methodology in 1995 and has been at the forefront in developing R-fcMRI applications for nearly two decades. Our group has previously used R-fcMRI to describe changes in neural networks in a variety of diseases and conditions, including cocaine/heroin abuse, mTBI, pain, Alzheimer's disease, depression, and anesthesia, etc. Also, MCI imaging research center, has a team of imaging physicists and imaging processing scientists and the-state-of-the- art GE MR750 3T scanner to conduct the proposed studies.

Outcome measure and Impact: The proposed study will provide biomarkers for the functional pathophysiology of functional GI disorders, as well as other comorbidities that can lead to improved diagnostic and treatment options for these debilitating conditions and ultimately improve the long-term health and welfare of functional GI disorders.

G. RISK CATEGORY:

Nausea and IBS patients - 45 CFR 46.405: Research involving greater than minimal risk but presenting the prospect of direct benefit to the individual child subjects

Healthy controls in fMRI sub-study - 45 CFR 46.404: Research not involving greater than minimal risk to the children

H. RISKS AND THE PRECAUTIONS WHICH WILL BE TAKEN TO MINIMIZE RISK EXPOSURE

Gastric function tests:

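### The only voxelwise measure and group test specified for the resting scans are task-fMRI methods applied within each group; the announced FN-versus-control connectivity comparison has no test

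*Combined protocol and SAP*

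**What the plan says.** Section B, Specific aim #2, states the hypothesis: "There will be decreased resting state functional connectivity between the ventromedial prefrontal cortex (vmPFC) and amygdala in adolescents with FN compared to healthy controls". Hypothesis 3b adds that active therapy will "increase the rsFC between the vmPFC and amygdala in female adolescents with FN", and Aim 3 sets healthy controls as the benchmark. Section C repeats the prediction for FN: "characterized by decreased rsFC between these regions in adolescent females with FN".

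Three places in section F plan a connectivity analysis.
- Resting State Functional Connectivity MRI defines rsFC as a correlation over time between a seed region and other regions, and takes the amygdala as the seed.
- The fMRI-guided connectivity analysis paragraph repeats the seed and adds the target areas.
- The Scanning protocol paragraph says rsFC will be compared before and after treatment, and with healthy controls and IBS patients.

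The Scanning protocol paragraph then turns to methods: "Brain activation will be quantified for each voxel by measuring percent change of BOLD signal relative to the baseline". At group level, "activation maps for each stimulation state and group will be derived by applying voxelwise one-sample" t-tests on a regression coefficient, with cluster-based correction.

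Under Power, Aim 2 has only a cross-reference to the fMRI analysis section. That section describes group-level analysis without naming a test, a Fisher discriminant, and a multivariate regression whose stated purpose ends with "in order to determine which subsets of the independent variables can be used to predict variations in cognitive ability across subjects".

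**The concern.** Percent signal change and activation maps per stimulation state belong to experiments in which a stimulus alternates with a baseline inside the scan. Here patients are scanned at rest, before the first device is placed and again after the last one is removed. The quantity and the test specified are therefore not the ones Aim 2 needs.

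An analyst who follows the text gets one map per group and may be tempted to read a region that is significant in controls but not in FN as a group difference. A subject-level measure, a vmPFC region and a contrast that are all left open, with 15 subjects per group, also leave room to choose them after seeing the data.

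**Working it through.** **1. What the hypothesis needs against what is specified**

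| Element | Needed for Aim 2 | Specified in section F |
|---|---|---|
| Measure | Amygdala-vmPFC correlation per subject | Percent BOLD change per voxel |
| Condition | Rest, baseline scan | Stimulation state |
| Group test | FN versus controls | One-sample t-test within each group |
| Region | A defined vmPFC region | Prefrontal areas, not delimited |

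A looser reading takes the baseline to be the pre-treatment scan and the stimulation state to be before or after therapy. This does not rescue the text. Controls have one scan, so no change can be computed for them, and a signal change is not a correlation between two regions. If the regression coefficient is a seed coefficient, the measure is right but the test is still within-group.

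**2. Inputs for the illustration**

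- n = 15 per group (section D, Optional fMRI Sub-study; section E).
- Alpha 0.05 (section O); two-sided is assumed, since the imaging text does not say.
- Effect sizes: none in the documents. The values below are assumptions.
- The plan has no imaging power or effect figure to reproduce.

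**3. Two one-sample tests when the groups do not differ**

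Let both groups have true mean connectivity d, in SD units from zero. The power w of each one-sample test comes from the noncentral t distribution with 14 df and noncentrality d√15. Then P(exactly one group significant) = 2w(1 − w), and P(controls significant, FN not) = w(1 − w).

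| d (assumed) | w | Exactly one significant | Controls yes, FN no |
|---|---|---|---|
| 0.3 | 0.190 | 31% | 15% |
| 0.5 | 0.438 | 49% | 25% |
| 0.8 | 0.821 | 29% | 15% |
| 1.0 | 0.949 | 10% | 5% |

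For d = 0.5: 2 × 0.438 × 0.562 = 0.492. At d = 1.2 the discordance is about 2%. A direct two-sided test rejects in 5% of such trials, so 2.5% in the hypothesised direction.

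**4. The converse**

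Let FN have d = 0.8 and controls 1.6, a true difference of 0.8 SD. Both one-sample tests are significant in about 82% of trials, so the two maps would look alike.

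**5. What the right test can detect**

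A two-sample t-test with 15 v 15 has 28 df and noncentrality d/√(1/15 + 1/15), where d is now the difference between groups. Power is 26% at d = 0.5, 56% at 0.8 and 75% at 1.0. It reaches 80% at d = 1.06.

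**The case against.** The strongest reply is that connectivity is planned. Section F defines rsFC, names the amygdala seed, and announces the comparison with controls in the sentence just before the activation text. The coefficient in the one-sample tests may well be a seed-regression coefficient. This stands, so a reader who infers that the trial measures only activation, or that no FN-versus-control comparison is intended, goes further than the documents allow. What remains is that the announced comparison has no specified statistic or test.

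A reader might also infer that the direction of benefit is ambiguous, because section C describes "increased vmPFC with concomitant decreased amygdala activity during successful emotional regulation", an inverse pattern. The documents do not support that. The same sentence goes on to link stronger coupling with healthier regulation. Sections B and C state the predicted direction, and Aim 3 names controls as the benchmark. Activity during emotional regulation is also not a resting correlation. Only the convention is open: whether coupling is signed or absolute, and what sign is expected in controls.

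The mentions of drug abuse and cognitive ability in the fMRI analyses section might suggest that the wrong populations and outcomes are being analysed. The section's own definitions say otherwise: the diseased group is nausea or pain subjects, and the dependent variables are clinical parameters. The stray terms look like leftover text. Even so, a classifier on a composite index is not a test of the Aim 2 connection.

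Finally, the percentages above are not the plan's error rate. They model one region at an uncorrected 0.05, whereas the plan uses cluster-corrected voxelwise tests, and no passage says a difference will be inferred from separate maps. The discordance also falls quickly above 0.8 SD.

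**Conclusion.** Wrong as written; should be fixed. The Scanning protocol paragraph specifies a measure that does not fit a resting scan and a test that does not compare groups. The section to which Aim 2 is referred does not supply the missing test. This conclusion rests on the text alone.

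The size is illustrative. With 15 per group, equal true means and two-sided 0.05, separate one-sample tests disagree in 49% to 29% of trials for assumed means of 0.5 to 0.8 SD, and in 10% at 1.0 SD. That is enough to show that within-group maps cannot stand in for the between-group test.

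It would be tempting to rank this higher because a whole specific aim depends on it. But the imaging is an optional sub-study, and the primary outcome, the Nausea Severity Scale total score, does not depend on it.

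**What to change.** In section F, Scanning protocol:

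- Delete the sentences on percent BOLD change and on activation maps by stimulation state.
- Define the subject-level endpoint as the Fisher-z correlation between the amygdala seed and a prespecified vmPFC region at the baseline scan.
- Test FN against healthy controls with a two-group test. Use the same two-group contrast for voxelwise maps, with the cluster correction already planned.
- Add one line saying that coupling is analysed as a signed value, giving the sign expected in controls, and reading 3b as movement toward the control mean, as Aim 3 already intends.

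As secondary clean-up in the fMRI analyses section, replace the drug-abuse and cognitive-ability wording with the trial's own groups (FN, IBS, controls) and scores it collects, such as the Nausea Severity Scale, the Nausea Profile and PROMIS anxiety.

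The cost is wording only, with no added scans or data. The change supplies the right test but no extra power: 15 v 15 still needs a difference of about 1.06 SD for 80% power.
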